16.0 SAMPLE SIZE

20 (10 control and 10 intervention) subjects who complete treatment/sham based on an estimate that this number will be sufficient to reveal whether this therapy is safe and whether further studies are warranted to investigate the level of any clinically meaningful pain relief.

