1.0 PURPOSE

Preliminary evaluation of the safety and effectiveness of Transcutaneous Magnetic Stimulation (TCMS) for the relief of low back pain.

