2.0 OBJECTIVE

To perform a preliminary study of the feasibility, safety, and effectiveness of TCMS for the relief of low back pain.

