8.0 INTERVENTION

Subjects will identify the location of pain on their back. A member of the study team will note the location on a drawing. The TCMS device will be placed at the site the patient

identified. (Low back pain is defined as pain below the costal margin posteriorly, extending as low as the upper buttocks.)

With only a hospital gown intervening, the clinician will place the active or sham TCMS device on the area of pain, turn the device on, and adjust the amplitude upward from 0.24T in increments of 10%, approximately every 6-10 seconds, until the 1.2T setting is achieved or the subject reports discomfort. If the patient reports discomfort, the amplitude will be adjusted downward as necessary to maintain patient comfort.

Treatment group: TCMS device set to 1.2 Tesla will deliver a dose of 10 pulses per minute for 9 minutes (total 90 pulses). The first minute will be dedicated to adjusting the amplitude until maximum is achieved and/or the subject reports a sensation.

Placebo group: the sham TCMS device will remain on the area of pain for 10 minutes. The sham TCMS device is engineered so as to make the same sound at the same intervals as the active device. The same procedures will occur as those with the active device. The first minute will be dedicated to adjusting the “sham” amplitude. The remaining 9 minutes will be the treatment period.

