11.0 DEFINITION OF SUCCESS

Treatment success is a 30% reduction in mean baseline pain score on the 0 to 10 Numeric Pain Rating Scale (NPRS) that persists at least 1 hour and occurs at any time in the period from treatment through 48-hour follow-up.

Study success is at least 3 of 10 treatment patients meeting the criteria for treatment success and no serious adverse events reported in any subject related to active treatment.

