12.0 EFFECTIVENESS OF ANALYSIS

Quantitative, but not statistically powered, trend-analysis of effectiveness of active treatment vs. sham.

Comparison of mean magnitude of treatment effect (change in NPRS) between sham and active treatment (cumulative responder analysis)

Medication usage

Non-drug treatment

Global Pain Scale (GPS)

Patient satisfaction with treatment

Presence of unwanted treatment effects, including paresthesia, irritation or discomfort, referred pain, and motor effects.

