14.0 SAFETY ANALYSIS

Qualitative tabular record of any AEs.

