26.0 DATA ANALYSIS

Descriptive statistics, trend analysis of endpoint means for effectiveness. Tabular collection of adverse events with narrative

STUDY SCHEDULE AND DESCRIPTION OF DATA COLLECTION

Time of data collection	Data collected						
	Log entry	Demographics	History	Informed consent	NPRS first rating or since last rating given	AE	Additional endpoints
*Eligibility screened and offered participation	X	X	X	X			
*Pain each day in 7-day period					X	X	
Day 1 (baseline = start of treatment)					X	X	X
During treatment: 5 minutes					X	X	
10 minutes					X	X	
After treatment: 1 hour					X	X	
2 hours					X	X	
3 hours					X	X	
4 hours					X	X	
8 hours					X	X	
12 hours					X	X	
24 hours					X	X	
48 hours					X	X	
72 hours					X	X	
*Final assessment 7 & 30 days (+3)		X (employment status only)			X	X	X

*Data can be collected in person, via mail, via telephone, email, or fax

LAY SUMMARY

The study will evaluate whether an experimental medical device that emits a brief, intense magnetic field will relieve pain in the low back. The United States Food and Drug Administration (FDA) has approved a similar device for treatment of migraine, but this type of device has not been studied for the treatment of low back pain. No significant adverse reactions or side effects have been reported from the use of magnetic stimulation for headache treatment. Some patients who have migraine headaches have excellent pain relief with the magnetic treatment even if they did not get pain relief with medications.

We do not know whether magnetic treatment will relieve low back pain, so we will test this by applying a powerful electromagnet to the painful area of the low back. In some subjects, the magnet will be turned on, but in other patients the magnet will not be turned on. Neither subjects nor subjects' treating doctor will know whether the magnet was turned on or not, although the study team will know which subjects received treatment with magnetic pulses. The effect on pain will be recorded periodically for 2 days. If the subjects' reported pain is reduced as a result of the magnetic treatment compared with subjects who did not have the magnet turned on, then the magnet might have reduced the pain. Additional studies will be needed to further investigate whether this therapy reduces low back pain.

Keywords: **low back pain, TCMS (Transcutaneous Magnetic Stimulation), TENS (Transcutaneous Electrical Nerve Stimulation)**

RATIONALE AND BACKGROUND

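### Section 16 says the sample size will show whether TCMS is safe, but zero related SAEs in 10 active patients would still be compatible with a true rate of up to 30.8%.

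*Combined protocol and SAP*

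**What the plan says.** Section 16 fixes the sample at 20 subjects who complete active or sham treatment, 10 per arm. Its only justification is that the number was chosen "based on an estimate that this number will be sufficient to reveal whether this therapy is safe and whether further studies are warranted". No assumed event rate, precision or tolerable upper limit accompanies this, in Section 16 or elsewhere.

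Section 11 makes safety one of two conditions for study success: "no serious adverse events reported in any subject related to active treatment". The other is at least 3 responders among the 10 treated patients.

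The planned safety reporting is descriptive. Section 14 offers a "Qualitative tabular record of any AEs" and Section 26 a "Tabular collection of adverse events with narrative". Section 12 lists "Presence of unwanted treatment effects, including paresthesia, irritation or discomfort, referred pain, and motor effects" among the items to be compared between active and sham. None of these sections plans an interval or names a safety population.

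The aims are more modest than Section 16. Section 1 speaks of a "Preliminary evaluation of the safety and effectiveness", and Section 2 says "To perform a preliminary study of the feasibility, safety, and effectiveness of TCMS".

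**The concern.** Section 16 attributes a property to the design: that this many subjects can settle whether the treatment is safe. Only the 10 active patients carry information on harm caused by active stimulation, and a clean record in 10 patients excludes only high event rates.

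This matters because of Section 11. A trial with no related SAE meets its safety condition, and Section 16 as written invites the reader to take that as a demonstration of safety. Nothing in Sections 12, 14 or 26 would correct that reading, since no proportion with an interval is planned.

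A second, smaller gap is the denominator. Section 16 counts completers. Section 17 excludes patients who cannot tolerate half of the maximum amplitude. That can be learned only once the device is running, because Section 8 has the clinician raise the amplitude "until the 1.2T setting is achieved or the subject reports discomfort". Section 23 replaces lost subjects. More people may therefore be exposed than the 20 who complete, and those excluded for intolerance are among the most informative about tolerability. The plan does not propose a completers-only safety analysis, but it does not rule one out.

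**Working it through.** **Inputs from the document**
- Active completers: 10 (Sections 16 and 20, Group Allocation).
- Event in the success rule: an SAE related to active treatment, with zero allowed (Section 11).
- Event rate, precision target, acceptable SAE rate: none given. The stated sample size therefore cannot be reproduced from any calculation.

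**Inputs assumed here**
- Two-sided 95% confidence, exact (Clopper-Pearson) method.
- True event rates of 1% to 30%, for illustration.
- 12 or 15 exposed active patients, to allow for replacements and exclusions.

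**Step 1: what zero events in n patients excludes.** The exact two-sided 95% upper limit is 1 − 0.025^(1/n).
- n = 10: 1 − 0.025^(1/10) = 0.3085, so the interval is 0 to 30.8%.
- n = 12: 0.2646, or 26.5%.
- n = 15: 0.2180, or 21.8%.

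Other methods for 0/10:
- One-sided 95% limit: 1 − 0.05^(1/10) = 25.9%.
- Wilson: 27.8%.
- Rule of three: 3/10 = 30%.

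Counting all 20 subjects would give 16.8%, but the 10 sham subjects receive no active stimulation.

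**Step 2: how often the Section 11 safety condition is met.** The chance of no related SAE in 10 active patients is (1 − p)^10.

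| True related-SAE rate p | Chance of none in 10 |
|---|---|
| 1% | 90% |
| 2% | 82% |
| 5% | 60% |
| 10% | 35% |
| 20% | 11% |

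With more patients exposed, the 5% row becomes 0.95^12 = 54% or 0.95^15 = 46%.

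**Step 3: what 10 patients can show.** The chance of at least one event is 1 − (1 − p)^10.
- 20% rate: 89%.
- 30% rate: 97%.
- For an 80% chance, p must be 1 − 0.2^(1/10) = 0.149, about 15%.

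**Step 4: scale.** With zero events, the number of exposed patients needed for a two-sided 95% upper limit below u is ln(0.025)/ln(1 − u), rounded up. For assumed limits of 10% and 5%, that is 36 and 72. These numbers show the distance from 10; they are not a proposal to enlarge the study.

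**The case against.** The best reply is that this is loose wording in a declared pilot. Sections 1 and 2 call the work preliminary, Section 12 disclaims power, and the Section 16 sentence goes on to whether further studies are worthwhile, so it can be read as a go/no-go statement. Any trial with 10 per arm would show the same limit for zero events. This stands as a defence of the sample size, which is not disputed. It does not rescue the claim: Section 16 carries no such qualification, and the Section 12 disclaimer concerns effectiveness only.

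The related SAE is also the endpoint on which 10 patients are weakest. Section 15 defines safety more widely: any undesirable sign or symptom, sensations during treatment, and device usability. For common effects the sample is informative, as Step 3 shows. That is right, and it is why the replacement wording should say so.

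The 60% figure is the chance of meeting one of two success conditions, not of study success, and it assumes exactly 10 exposed. Section 23 also suspends enrolment after any SAE. Both points are correct, but neither changes what a zero count can exclude.

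On the denominator, Sections 11 and 14 refer to any subject and any AE, and Section 23 asks withdrawn subjects to keep supplying data. These point towards counting everyone, but no population is named. Section 17 does not say whether the tolerance exclusion comes before or after randomisation. However, Section 8 describes the amplitude adjustment on the active or sham device itself, so a denominator based on that device being switched on would include intolerant patients.

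Finally, descriptive listing is a legitimate choice at this size, and the 95% level is a convention. Intervals are asked for only because Sections 11 and 16 attach a safety conclusion to the counts.

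**Conclusion.** The concern holds. Section 16 claims that the sample can settle whether the treatment is safe, and the sample cannot do so. No related SAE in 10 active patients would be compatible with true rates up to 30.8% (exact, two-sided 95%); the other methods give upper limits of 25.9% to 30%. If 12 or 15 active patients were exposed, the exact limit would be 26.5% or 21.8%, and the conclusion would be the same.

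This is an unsupported justification of the sample size, not an arithmetic error, and it gives no reason to change the number of patients. It should be corrected because it affects how a zero-SAE result under Section 11 would be read. The missing safety population, taken alone, is a lack of detail. The result rests on 10 patients exposed to active stimulation and on the usual 95% level. The rates in Steps 2 and 3 are illustrative, since the document gives none.

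**What to change.** **Section 16.** Replace the safety clause and keep the clause on whether further studies are warranted. Suggested wording:

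> The study gives preliminary safety data on common adverse effects. If no related SAE is seen in 10 active patients, the exact two-sided 95% CI for the rate is 0 to 30.8%, so the study cannot establish safety.

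**Section 14.** Keep the qualitative table and narratives. Add, by arm, the number and proportion of subjects with:
1. any AE;
2. any SAE;
3. any treatment-related SAE (in the active arm, the quantity used in Section 11).

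Give each an exact (Clopper-Pearson) two-sided 95% CI. State the denominator as everyone in whom the assigned active or sham device was switched on, including those later excluded for intolerance, lost or replaced.

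Leave Section 11 as written.

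**Cost.** Wording in two sections and one small table of three outcomes by two arms, with no added patients or visits. The safety claim the study can make becomes less favourable.

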17.0 RECRUITMENT, ENROLLMENT, AND ELIGIBILITY CONFIRMATION

All potential subjects identified through standard clinical practice at the site will be listed on a Screening Log and provided with detailed study information, including a description of TCMS.

We anticipate that 350 patients will be screened and 20 patients will be randomized to either placebo or intervention

If the subject is willing to participate, written informed consent will be obtained.

A subject is considered provisionally enrolled upon completion of the informed consent process.

Subjects provisionally enrolled will be taught how to complete a 7-day diary recording low back pain and will complete this diary before randomization (Self-Report).

Subjects will not be told the pain scores are needed for study inclusion.

The principal investigator or a member of the study team will review the diary to confirm that the subject's mean pain intensity score meets the inclusion criteria. Subjects who do not complete the diary or who fail to meet preliminary pain eligibility requirements will not be randomized, are ineligible for participation in the study and will not be counted in the number of enrolled patients. In such cases, the principal investigator or an authorized designee will log this into the data collection system.

If a patient is unable to tolerate at least 50% of the max 1.2T they will be excluded from the study.

** A significant change for this study is defined as a 20% increase or decrease in dosing of the patient's opioid dose and/or or a change in the medication class (adding or removing other types of medicine used to treat pain).*

*** This exclusion is restricted to opioids, benzodiazepines and psychotropics.*

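### The 50% tolerance exclusion falls after randomisation and, for field intolerance, only on the active arm, so a completer count would rest the 3-of-10 rule and the sham comparison on a tolerance-selected active group.

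*Combined protocol and SAP*

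**What the plan says.** - **Exclusion rule.** Section 17.0, under eligibility confirmation: "If a patient is unable to tolerate at least 50% of the max 1.2T they will be excluded from the study". It gives no timing, names no arm, and does not say how such subjects are counted or replaced.
- **Ramp.** In Section 8.0 the clinician places the active or sham device and is to "adjust the amplitude upward from 0.24T in increments of 10" per cent, up to 1.2T or until discomfort. The section continues: "If the patient reports discomfort, the amplitude will be adjusted downward as necessary to maintain patient comfort". It does not mention exclusion.
- **Sham.** Section 8.0 says of the sham arm: "The same procedures will occur as those with the active device". The lay summary says the magnet is not turned on in these subjects.
- **Order of events.** Section 19.0 and the schedule of events put randomisation before treatment. The data collection table in Section 26.0 shows no stimulation before Day 1.
- **Success and comparison.** Section 11.0: "Study success is at least 3 of 10 treatment patients meeting the criteria for treatment success", together with a safety condition. Section 12.0: "Comparison of mean magnitude of treatment effect (change in NPRS) between sham and active treatment".
- **Counting.** Section 16.0 sets the sample at "20 (10 control and 10 intervention) subjects who complete treatment/sham". Section 17.0 says "We anticipate that 350 patients will be screened and 20 patients will be randomized to either placebo or intervention". Section 23.0 replaces randomised subjects who are lost, without defining the term, and asks withdrawn subjects to keep completing questionnaires. Group Allocation (the first of two sections numbered 20.0) uses the numbers 1 to 20.

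**The concern.** A tolerance criterion applied before randomisation affects both arms alike. Here the criterion can be observed only once the assigned device is running, and the stimulus that would cause field intolerance is present in one arm only. Subjects removed at that point leave an active group selected on a response to the active field, compared with a sham group that has not been selected in the same way.

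Two results depend on this. The 3-of-10 rule is the only numerical effectiveness criterion for study success, and with ten subjects one person can decide it. The comparison of mean NPRS change relies on randomisation to make the arms alike, and exclusion after randomisation can undo that.

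**Working it through.** **Step 1. When can the rule operate?** The threshold is 50% × 1.2T = 0.6T. The ramp starts at 0.24T, which is 0.24/1.2 = 20% of maximum, so the threshold is reached only during the ramp. If the 10% increment means 10% of 1.2T (0.12T), it is reached after (0.6 − 0.24)/0.12 = 3 steps. At 6 to 10 seconds each, that is 18 to 30 seconds into the assigned session. Whatever the increment means, the ramp begins below the threshold and is on the assigned device. The pre-randomisation check described in Section 17.0 is the diary and pain score. No test exposure is described anywhere.

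**Step 2. Which arm?** With the sham magnet off, intolerance of the field cannot occur there. A sham subject could report discomfort from another cause, and the rule would then apply on paper.

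**Step 3. Size for the 3-of-10 rule.** The plan gives no intolerance rate, expected response rate, alpha or power, so there is no figure of its own to reproduce. Everything below is an assumption, shown over a range.

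- t = proportion of active subjects excluded: 2%, 5%, 10%, 20%, 30%
- p = response rate among tolerators: 10% to 50%
- r = response rate among excluded subjects, first set to 0

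Completers with replacement: P(Bin(10, p) ≥ 3). First 10 randomised to active: P(Bin(10, p(1 − t) + rt) ≥ 3). The gap is the first minus the second.

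| p | Completers | Gap, t = 2% | 5% | 10% | 20% | 30% |
|---|---|---|---|---|---|---|
| 10% | 0.070 | 0.003 | 0.008 | 0.016 | 0.030 | 0.042 |
| 20% | 0.322 | 0.012 | 0.030 | 0.059 | 0.116 | 0.168 |
| 30% | 0.617 | 0.016 | 0.041 | 0.084 | 0.173 | 0.265 |
| 40% | 0.833 | 0.013 | 0.034 | 0.073 | 0.164 | 0.271 |
| 50% | 0.945 | 0.007 | 0.020 | 0.045 | 0.113 | 0.207 |

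Example: p = 30%, t = 10%, r = 0 gives a rate of 0.30 × 0.90 = 0.27 in the first 10. P(Bin(10, 0.27) ≥ 3) = 0.534, and 0.617 − 0.534 = 0.084 before rounding of the terms.

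**Step 4. What weakens it (p = 30%).**

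- Excluded subjects replaced and responding at 10%: the gap falls to 0.011, 0.027, 0.055, 0.113 and 0.173 across the five values of t.
- Excluded subjects replaced and responding at 30%: the gap is zero.
- Not replaced, r = 0: completers and the first 10 have the same number of successes, so the gap is zero.
- Not replaced, r = 10% with NPRS observed: the first-10 count passes more often, by 0.005 to 0.092.

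**Step 5. Would the question arise at all?** The chance of at least one exclusion among 10 active subjects is 1 − (1 − t)^10 = 0.183, 0.401, 0.651, 0.893 and 0.972.

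**Step 6. Denominators.** With k = 1, 2 or 3 excluded and replaced, three responders are 3/10 by the rule but 3/11 = 27%, 3/12 = 25% or 3/13 = 23% of those randomised to active.

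**Step 7. Mean NPRS change.** In the active arm, the completer mean minus the all-randomised mean equals t × (mean change in tolerators − mean change in excluded subjects). That is 0.02 to 0.30 points per 1-point difference. Its sign cannot be derived from the documents.

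**The case against.** The strongest reply is that the plan does indicate how subjects are counted. A reader might infer that it is silent. It is not: Section 16.0 defines the ten per arm as completers and Section 23.0 provides for replacement. This stands, and it limits what can be claimed. It does not remove the concern, because a completer count with replacement is the very case that yields the selected arm. What stays open is whether a subject excluded under the 50% rule counts as lost.

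A reader might also infer that Sections 16.0 and 17.0 contradict each other on the number 20, or that the allocation numbers rule out replacement. Neither follows. The 20 randomised in Section 17.0 is a forecast, and nothing forbids randomising more or reusing a vacated number. The wording needs reconciling, no more.

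A third tempting inference is that the plan is biased in favour of active treatment. The documents do not fix the direction: Step 4 shows gaps of zero and of the opposite sign.

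On size, the background section expects little skin pain, and Section 8.0 lowers the amplitude for comfort, so exclusions may be rare. The largest gaps need 30% intolerance and no response among those excluded, and no section supports either. Sections 9.5, 14.0 and 15.0 already require discomfort and adverse events to be recorded, and the safety half of study success is not confined to ten completers. These points stand. What is not specified is a count of tolerance exclusions by arm.

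Finally, response among those actually treated is a legitimate target in a preliminary, unpowered study. That also stands, so the documents do not support insisting that the first 10 randomised be the sole basis for 3 of 10.

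**Conclusion.** The concern holds in limited form and is minor. As scheduled, the 50% rule removes subjects after randomisation, and removal for field intolerance can occur only in the active arm. On the reading that Sections 16.0 and 23.0 favour, the 3-of-10 rule and the active-sham NPRS comparison rest on a tolerance-selected active arm.

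The size cannot be known from the documents. With replacement and no response among excluded subjects, the change in the chance of passing runs from 0.003 (10% response, 2% intolerance) to 0.271 (40% response, 30% intolerance). It shrinks as excluded subjects respond more like tolerators. The conclusion about timing rests on the absence of any described device exposure before randomisation. The conclusion about the arm rests on the lay summary's description of the sham.

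**What to change.** In Sections 11.0, 12.0, 16.0, 17.0 and 23.0:

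1. Summarise NPRS change and responder status for every randomised subject in the assigned arm, using all NPRS data obtained, and show the completer summary beside it. Extend the Section 23.0 request for continued questionnaires to subjects excluded under the 50% rule, since it now speaks only of withdrawn subjects.
2. Report the 3-of-10 result with both the number randomised to active and the number completing. State in advance which count decides study success.
3. Report by arm the number excluded for not reaching 50% output and the number with no NPRS data.
4. Reconcile Section 8.0 (amplitude lowered for comfort) with Section 17.0 (exclusion), including how the rule applies to sham. Reconcile Sections 16.0, 17.0, 20.0 (Group Allocation) and 23.0 on replacement and on whether 20 is the number randomised or completing. No clinical rule is proposed here.

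The cost is protocol wording, one extra summary, continued follow-up of any excluded subjects, and a responder proportion that may look less favourable.
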